### 9.2. Selection of Timing of Dose for Each Subject

The IP will be administered once in each nostril. Men and women will be treated with the same 3.2- $\mu$ g dose of PH94B. Each nasal spray delivers 100  $\mu$ L containing 1.6  $\mu$ g PH94B. [REDACTED]

Treatment with PH94B should be self-administered approximately 15 minutes prior to or during an anxiety-provoking social situation or event. Consecutive nasal administrations of IP should be at least 1 hour apart, with no more than 4 administrations per day.

Site personnel will instruct the subject to self-administer the IP by 1 spray into each nostril (right and left nasal passages), for 2 total sprays per dosing event.

Subjects are instructed to record all PH94B administrations in the provided eDiary, even if they have not used PH94B that day (see Section 9.4.1).

### 9.3. Dose Adjustment Criteria

Dose adjustment is not allowed in this study.

### 9.4. Treatment Compliance

Study personnel will weigh each vial of IP prior to dispensing to subjects and upon return of used or unused vials of IP from subjects to the study personnel. Vial weights will be documented in the eCRF. Subjects will record their use of the IP in an eDiary during the study (see Section 9.4.1).

Subjects will self-administer the IP up to 4 times per day between visits. The study personnel will be responsible for reviewing the self-administration of the IP in the eDiary.

#### **9.4.1 eDiary**

Subjects participating in the study will be instructed to record their use of PH94B in an eDiary application. The eDiary will be made available to subjects as an “application” to be downloaded and used on their smartphone or a similar device.

Subjects will be instructed to complete the eDiary at the end of each day even if zero doses are taken that day. They will be instructed to provide information on the number of doses they self-administered that day and the approximate time of each dose.

After the subject has completed the dosing section, the eDiary will prompt the subject to answer if they have experienced any health problems that day. If they answer yes, the subject is asked to write a brief summary text in the eDiary. The Investigator or a delegate will review these summary texts at each visit and determine whether they are to be recorded in the EDC system as AEs, with their severity, duration, and relationship to the study drug.

A nominal payment will be made to subjects for each day that they complete the eDiary. This will be made available to the subject at the end of the study.

At each study visit from Visit 3 through Visit 14, study staff will review the subject’s eDiary entries. Additional training on the use of the eDiary may be administered if necessary (see Section 9.4).

#### **9.5. Method of Assigning Subjects to Treatment Groups**

In this open-label, single-treatment study, all subjects will receive the same treatment.

Subject numbers will be allocated by the IRT. Subjects will be sequentially assigned 6-digit numbers as shown below. The subject number will include the site number. Instructions on subject number assignments will be included in the IRT manual.

Sourcea	Site Number	Subject ID	Example
New Subjects b	001	Starting with 001	001-001 001-002
PALISADE-1 Study (Completers)	001	Starting with 101	001-101 001-102
PALISADE-2 Study (Completers)	001	Starting with 501	001-501 001-502

a Participants from other antecedent studies will follow a similar systematic numbering convention.

b Subjects who have not participated in a prior PH94B SAD study may be permitted to enroll following approval by the sponsor on a case-by-case basis.

#### **9.6. Blinding and Unblinding Treatment Assignment**

Not applicable – this is an open-label study with all subjects receiving PH94B.

#### **9.7. Permitted and Prohibited Therapies**

[figure not shown]
All medications taken by or administered to the subject during the month prior to Screening (Visit 1) should be recorded in the eCRF. All concomitant medication taken during the study will be recorded on appropriate pages of the eCRF.

In order to ensure that appropriate concomitant therapy is administered, it is essential that subjects be instructed not to take any medication (either self-administered non-prescription drugs or prescription therapy prescribed by another physician) without prior consultation with the Investigator. The Investigator should examine the acceptability of all concomitant medications not explicitly prohibited. Sites should contact the Medical Monitor when uncertain about the acceptability of concomitant medications. All concomitant medication taken during the study will be recorded on appropriate pages of the eCRF.

### **9.7.1 Permitted Therapies**

With the exception of those noted in Section 9.7.2, all medications (prescription or over-the-counter) that were started prior to Screening may be continued during the course of the study. During the course of the study, subjects should stay on stable doses of their usual allowable medication regimens. Medications for treatment of minor concurrent illnesses that arise after Screening may be allowed at the discretion of the Investigator, with the exception of the prohibited therapies specified in Section 9.7.2.

The use of eszopiclone, ramelteon, melatonin, zaleplon, zolpidem, or anti-histamines as concomitant medications for the treatment of insomnia is permitted.

Investigators may allow concomitant use of over-the-counter nasal decongestants as needed for seasonal allergies. Subjects may self-administer over-the-counter nasal decongestants at a minimum of 15 minutes prior to the use of IP during the study.

In general, starting treatment with antidepressants and buspirone during the study is allowed but the investigator should inform the Medical Monitor of this decision; for antidepressants, initiating treatment is permitted provided that the antidepressant has been approved for the treatment of SAD or major depressive disorder by the FDA. However, while subjects may begin treatment with antidepressants, use of MAO inhibitors or ketamine is not permitted.

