#### 8.2.2 Exclusion Criteria

To be considered eligible for entry into the study, a subject must not meet any of the following exclusion criteria at study entry.

1. Any history of bipolar disorder (I or II), schizophrenia, schizoaffective disorder, psychosis, anorexia or bulimia, premenstrual dysphoric disorder, autism-spectrum disorder, obsessive-compulsive disorder, or treatment-refractory major depressive disorder.

Any other current Axis I disorder, other than SAD, which is the primary focus of treatment. Note that subjects with concurrent Generalized Anxiety Disorder are eligible for the study provided that Generalized Anxiety Disorder is not the primary diagnosis.

2. In the opinion of the Investigator, the subject has a significant risk for suicidal behavior during the course of their participation in the study, or
  - a. At Screening (for subjects who attend Visit 1): the subject scores “yes” on items 4 or 5 in the Suicidal Ideation section of the Columbia-Suicide Severity Rating Scale (C-SSRS) with reference to a 6-month period prior to screening; or
  - b. At Screening (for subjects who attend Visit 1): the subject has had 1 or more suicidal attempts with reference to a 2-year period prior to screening; or
  - c. At Baseline (Visit 2): the subject scores “yes” on items 4 or 5 in the Suicidal Ideation section of the C-SSRS with reference to last visit; or
  - d. The subject is considered to be an imminent danger to themselves or others.
3. Subjects using the following psychotropic medications at enrollment or within 30 days before study entry: antidepressants (including monoamine oxidase [MAO] inhibitors), anxiolytics, stimulants, anticonvulsants, mood stabilizers, antipsychotic medications, gabapentin, pregabalin, opioids, naltrexone, esketamine, and ketamine. Eszopiclone, ramelteon, melatonin, zaleplon, zolpidem, or anti-histamines prescribed for insomnia are allowed.
4. Use of benzodiazepines or unapproved treatments such as beta blockers, within 30 days before study entry and during the study. Use of beta blockers for treatment of hypertension or cardiac conditions is allowed. Subjects who have been taking benzodiazepines daily for 1 month or longer at the time of Visit 1 are not eligible to participate.
5. Use of any over-the-counter product or herbal preparation for treatment of the symptoms of anxiety or social anxiety within 30 days before study entry; concomitant use is prohibited during the study.

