### **9.7.2 Prohibited Therapies**

At Screening (Visit 1), the Investigator may consider checking the local Prescription Drug Monitoring Database to confirm that subjects are not using scheduled central nervous system active drugs, such as benzodiazepines, if appropriate.

For subjects who use a prohibited medication (see below) during the study, Investigators should discuss the subject with the Medical Monitor. Such treatment might not be a cause for discontinuing the subject from the study. In particular, one-time use or very short-term use ( $\leq 3$  days) of prohibited medications, e.g., in cases of legitimate medical requirement such as minor surgeries or procedures, will not necessarily lead to exclusion from the study. These subjects should be discussed on a case-by-case basis with the Medical Monitor.

Prohibited medications are as follows:

- Prior use of PH94B is not permitted, except for subjects who have participated in a PH94B SAD study.

- Use of the following psychotropic medications is prohibited: anxiolytics, anticonvulsants, mood stabilizers, antipsychotic medications, stimulants, gabapentin, pregabalin, opioids, naltrexone, esketamine, and ketamine.
  - Use of antidepressants is prohibited at enrollment or within 30 days before the study. However, treatment with antidepressants or buspirone can be initiated during the study (see Section 9.7.1).  
Note: Treatment with MAO inhibitors or ketamine is prohibited at all times.
- Use of benzodiazepines and unapproved anxiety treatments such as beta blockers is not permitted within 30 days before study entry (Visit 2), or during the study.
  - Subjects requiring daily treatment with benzodiazepines are excluded from the study. If a subject develops the need to use benzodiazepines for management of anxiety, their participation in the study will be discontinued and the subject will be excluded from the study.
  - Use of beta blockers for treatment of hypertension or cardiac conditions is allowed.
- Use of any over-the-counter product or herbal preparation for treatment of the symptoms of anxiety or social anxiety is not permitted within 30 days before study entry, or during the study.

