#### 13.1.1 Analysis Populations

A single analysis population is planned for this study:

- Safety population: All subjects who receive IP.

All analyses will be performed using the Safety population.

Primary and exploratory endpoints may be summarized by subgroups of interest including age, sex, concomitant medications, and SAD severity. Analysis of subgroups not pre-defined in the final SAP will be labeled as such in the clinical study report (CSR).

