#### 13.1.5.1 Exploratory Endpoints

Overall subject improvement as assessed by the clinician's rating on LSAS, CGI-S, CGI-I, and the subject's rating of the PGI-C from Screening (Visit 1) through Follow-up (Visit 15) will be summarized, including changes from baseline where appropriate. The change in LSAS, CGI-I, and PGI-C scores from Baseline to Visit 14 may also be explored using generalized linear model for repeated measures.

In addition, overall change in the pattern in the frequency of PH94B use (frequent users; 3 or 4 times a day and less frequent users;  $\leq$  2 times a day), change in medication use as documented by the clinician and the subject between Screening (Visit 1) and Follow-up (Visit 15) will be summarized.

Full details on this exploratory analysis will be provided in the SAP.

The exploratory endpoints are as follows:

- Change in total LSAS scores over time with use of PH94B
- Change in proportion of subjects with CGI-S scores  $>4$  over time with use of PH94B
- Change in proportion of subjects with CGI-I scores of 1 (Very much improved) or 2 (Much improved) over time with use of PH94B
- Change in proportion of subjects with PGI-C scores of 1 (Very much improved) or 2 (Much improved) over time with use of PH94B
- [REDACTED]
- [REDACTED]
- [REDACTED]

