7.5. Exploratory Efficacy Analysis

All exploratory endpoints will be summarized for descriptive purposes only.

The following variables will be summarized for all subjects completing each visit. All derived variables will be computed as described in Section 0.

Categorical data will report frequency of responses and proportion of responders by study visit:

1. Proportion of CGI-I responders will be assessed from Visit 3 to Visit 14 by study visit.
2. Change in proportion of PGI-C responders will be assessed from Visit 3 to Visit 14 by study visit.
3. Proportion of CGI-S scores > 4 by from Visit 2 to Visit 14 by study visit.

Continuous data will report descriptive statistics of observed values and change from baseline by study visit:

4. Change in LSAS total scores by visit.
5. [REDACTED]

8. Safety and Tolerability Analysis

Safety in this study will be evaluated based on data collected on AEs, clinical laboratory assessments, vital signs, 12-lead ECGs, PWC-20 (at Visit 14/15 End of Study/Follow-up), and physical examinations including examination of the nasal passages. As a precautionary measure, subjects will also be assessed using the C-SSRS and HAM-D at each study Visit.

All safety analysis reporting will be based on the Safety Population (as defined in Section **Error! Reference source not found.**). No formal statistical testing will be conducted for the safety analyses. Descriptive statistics will be used to evaluate safety data. Summaries will present data by overall subjects. Listings will list safety data by subject.

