8.8. Hamilton Depression Scale (HAM-D)

Total scores and change from baseline will be summarized for the Safety population.

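### Scores recorded after an on-study antidepressant or buspirone start are pooled with all others, and no planned table links a start to the scores

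*Protocol*

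**What the plan says.** **Entry.** Exclusion criterion 3 (Protocol 8.2.2) bars "Subjects using the following psychotropic medications at enrollment or within 30 days before study entry: antidepressants", with anxiolytics among the other classes listed. Apart from entry deviations, any antidepressant or buspirone use is therefore a post-baseline start.

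**On study.** Protocol 9.7.1 states that "starting treatment with antidepressants and buspirone during the study is allowed", and the investigator informs the Medical Monitor. For antidepressants, "initiating treatment is permitted provided that the antidepressant has been approved for the treatment of SAD or major depressive disorder by the FDA"; MAO inhibitors and ketamine stay barred. Protocol 9.7.2 agrees: "treatment with antidepressants or buspirone can be initiated during the study".

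**Efficacy scales.** Protocol 13.1.5.1 words the first exploratory endpoint as "Change in total LSAS scores over time with use of PH94B". SAP 7.5 plans "Change in LSAS total scores by visit", plus by-visit summaries of CGI-S, CGI-I and PGI-C, for everyone who completes the visit in question.

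**HAM-D17.** SAP 8.8 reads: "Total scores and change from baseline will be summarized for the Safety population". Level of depression is named in the primary objective (Protocol 6.1, SAP 2.1.1), and HAM-D17 change is a safety endpoint (Protocol 13.1.4, SAP 2.2.1).

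**General rules.** SAP 6.1.4 uses observed data only, and SAP 6.1.2 has no covariate adjustment.

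**Medication.** Protocol 13.1.1 says endpoints "may be summarized by subgroups of interest including age, sex, concomitant medications, and SAD severity". Protocol 13.1.5.1 commits to summarising change in medication use from Visit 1 to Visit 15. SAP 8.5 gives counts by ATC class and preferred term.

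**The concern.** Starting an antidepressant or buspirone is an intercurrent event that can change the very scales being summarised. The permission covers drugs approved for SAD itself, and Protocol 5.1.1 names antidepressants among current SAD treatments. The SAP has no rule for the event.

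Two readings are affected. For LSAS and the global scales, starts accumulate over 12 months. If starters remain in the study, their share grows at later visits, and benefit from the added drug could look like sustained or growing change on PH94B. For HAM-D17, a subject who worsens, starts a drug and improves contributes favourable later scores, so the later-visit means understate how much depression worsened. The second matters more, because depression is part of the primary safety objective.

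**Working it through.** The plan states no figure to reproduce. The sample size of up to 600 is set by safety-exposure needs (Protocol 13.2, SAP 3.2), with no effect size, SD or dropout rate.

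**1. Does any planned output link starts to scores?**
- SAP 8.5 and Table 14.3.6.4 count subjects by drug. Given the entry exclusions, the antidepressant and buspirone rows are close to a count of starts. They give no timing and no scores.
- Table 14.5.1 gives HAM-D by visit for everyone, without reference to medication.
- Listings 16.2.9.5 (medications) and 16.2.9.7 (HAM-D) hold the raw data in separate places, so a reader would have to match them by hand.
- The SAP's readable text takes up neither the optional subgroup in Protocol 13.1.1 nor the medication-change summary in Protocol 13.1.5.1, and SAP section 10 does not list either as dropped. SAP 12.2 is an empty heading in the available text and one item in SAP 7.5 is redacted, so this holds for the readable text only.

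**2. How far could pooling move a mean?** Let f be the share of subjects at a visit who have started such a drug, and d the extra improvement it gives.

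Shift in mean change = f × d. Shift in responder proportion = f × dp.

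Every value of f, d and dp below is an assumption.

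| f | Starters if n = 600 | LSAS, d = 5 to 20 points | CGI-I or PGI-C response, dp = 10 to 30 percentage points | HAM-D17, d = 1 to 4 points |
|---|---|---|---|---|
| 5% | 30 | 0.25 to 1.0 | 0.5 to 1.5 | 0.05 to 0.2 |
| 10% | 60 | 0.5 to 2.0 | 1 to 3 | 0.1 to 0.4 |
| 20% | 120 | 1.0 to 4.0 | 2 to 6 | 0.2 to 0.8 |
| 30% | 180 | 1.5 to 6.0 | 3 to 9 | 0.3 to 1.2 |

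For example, 0.05 × 5 = 0.25 and 0.30 × 20 = 6.0.

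**3. Compared with sampling error.** The 95% half-width for mean LSAS change is 1.96 × SD / √n. With an assumed SD of 25 this is 4.9 (n = 100), 2.8 (n = 300) and 2.0 (n = 600). At 5% uptake the shift is below sampling error at all three sizes. At 20% to 30% uptake with a large effect it can exceed it. The formula gives every starter the full gain at the visit summarised, so late starts, dropout and partial response would make the shift smaller.

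**4. What would each HAM-D17 summary show for a subject who worsens, starts a drug and then improves?**
- All observed data: the high score stays at its own visit, and the improved scores enter later visits.
- Scores set to missing after the start: the subject leaves the later means altogether, so those means can also look better.
- Last score before the start, and worst post-baseline change: both keep the worsening visible. HAM-D17 is scheduled at every visit from Screening to Visit 14 (SAP Table 1), so a recent pre-start value should normally exist.

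**5. Are start dates usable?** On-study medications are recorded in the eCRF (Protocol 9.7). Under SAP 6.1.8, an onset missing both month and day is placed in the month of first dose. Removing scores from that date would delete nearly all of the subject's post-baseline data.

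**The case against.** The strongest reply is that depression is already watched in several ways. HAM-D17 is tabulated by visit and listed by subject, so later treatment cannot erase a pre-start score. Worsening of a pre-existing condition is an adverse event (Protocol 11.1.1), as are clinically relevant findings at a visit (Protocol 11.2.1). An event that leads to significant added therapy is a significant adverse event (Protocol 11.1.4). TEAEs and C-SSRS results are summarised (SAP 8.1, 8.6). All of this stands. A reader might infer that the plan hides worsening depression; the documents do not support that, only dilution at later visits.

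A reader might also infer that the plan credits the added drug's benefit to PH94B. The protocol's endpoint wording invites this, but the study is open-label without a comparator, efficacy is exploratory (Protocol 7.2), and SAP 7.5 is descriptive only. No PH94B effect is identified with or without this change.

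Nor does leaving out the concomitant-medication subgroup contradict the protocol, which makes it optional. The medication-change sentence in Protocol 13.1.5.1 is firmer, but it does not ask for a link to scores.

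Finally, dropping scores after a start is informative censoring, because those who need another drug may be those doing worse. That also stands, and it rules out censoring as the remedy for HAM-D17.

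**Conclusion.** The point holds as a gap in the analysis plan. Starts are allowed after a drug-free entry, later scores are pooled, and no planned table in the readable text connects the two. Later-visit means for LSAS, CGI-S, CGI-I, PGI-C and HAM-D17 can therefore mix in the added drug's effect, and evidence of worsening depression can be diluted.

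The size cannot be known from the documents. On the assumed inputs, the LSAS shift runs from 0.25 points (5% uptake, 5 extra points) to 6.0 (30% uptake, 20 extra points), and the HAM-D17 shift from 0.05 to 1.2 points. No confirmatory conclusion depends on this. It should be changed because the change is cheap and improves what the trial can say about depression. Whether these drugs should be permitted is a clinical matter and is not judged here.

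**What to change.** Keep the all-data summaries as they are, and add the following.

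- **SAP 8.8:** tabulate the number and timing of on-study antidepressant and buspirone starts, with the last HAM-D17 score and change from baseline before each start. Add each subject's worst post-baseline HAM-D17 change. Do not rely on setting HAM-D17 to missing after a start.
- **SAP 7.5:** add a supportive LSAS, CGI-S, CGI-I and PGI-C summary restricted to scores before any start. Show it beside the all-data summary and label it as selective, because subjects who start a drug may be those doing worse.
- **Dates:** flag starts with month and day both missing. Do not use the SAP 6.1.8 imputed date to remove scores.

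The cost is a few extra tables from data already recorded, and a supportive subset that is smaller and selective. If the tables are added after data have been examined, SAP section 1 already provides for identifying them as post hoc.

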### **9.7.2 Prohibited Therapies**

At Screening (Visit 1), the Investigator may consider checking the local Prescription Drug Monitoring Database to confirm that subjects are not using scheduled central nervous system active drugs, such as benzodiazepines, if appropriate.

For subjects who use a prohibited medication (see below) during the study, Investigators should discuss the subject with the Medical Monitor. Such treatment might not be a cause for discontinuing the subject from the study. In particular, one-time use or very short-term use ( $\leq 3$  days) of prohibited medications, e.g., in cases of legitimate medical requirement such as minor surgeries or procedures, will not necessarily lead to exclusion from the study. These subjects should be discussed on a case-by-case basis with the Medical Monitor.

Prohibited medications are as follows:

- Prior use of PH94B is not permitted, except for subjects who have participated in a PH94B SAD study.

- Use of the following psychotropic medications is prohibited: anxiolytics, anticonvulsants, mood stabilizers, antipsychotic medications, stimulants, gabapentin, pregabalin, opioids, naltrexone, esketamine, and ketamine.
  - Use of antidepressants is prohibited at enrollment or within 30 days before the study. However, treatment with antidepressants or buspirone can be initiated during the study (see Section 9.7.1).  
Note: Treatment with MAO inhibitors or ketamine is prohibited at all times.
- Use of benzodiazepines and unapproved anxiety treatments such as beta blockers is not permitted within 30 days before study entry (Visit 2), or during the study.
  - Subjects requiring daily treatment with benzodiazepines are excluded from the study. If a subject develops the need to use benzodiazepines for management of anxiety, their participation in the study will be discontinued and the subject will be excluded from the study.
  - Use of beta blockers for treatment of hypertension or cardiac conditions is allowed.
- Use of any over-the-counter product or herbal preparation for treatment of the symptoms of anxiety or social anxiety is not permitted within 30 days before study entry, or during the study.

Where washout of prohibited medications is required before Visit 2 (Baseline), tapering rates are at the discretion of the Investigator and are to be determined on an individual basis, with consideration to subject state, dose, and known pharmacokinetics of the medication being discontinued. The subject must be consented before any tapering is started.

